
Based on the simple effects and correlation power analyses above, we propose to collect 30 PD subjects per group (total 60) to account for potential subject dropouts, experimental/data corruption and/or an unexpected increase in the variability of the data. We plan to recruit about 100 subjects to take into account potential drop-outs and an unexpected increase in the variability of the data which impacts the estimated statistical power.
			
c. Describe how data and specimens will be handled:			 N/A
i. What information will be included in that data or associated with the specimens?			
	Please refer to 6a above. All data will be coded.		
ii. Where and how data and/or specimens will be stored?			
	Specimens: Core lab. Data: Secured computer. ICD will be stored in a locked cabinet. NOTE: All data including specimens will be coded.		
iii. How long will the data and/or specimens be stored?			
	Indefinitely		
iv. Who will have access to the data or specimens?			
	Research team		
v. Who is responsible for receipt or transmission of the data and/or specimens?			
	[name] (PI)		
vi. How will data and/or specimens be transported?			
	Manually		

8. Provisions to Monitor the Data to Ensure the Safety of Subjects

This study involves no more than minimal risk study and this section is not required. **N/A**

The plan might include establishing a data monitoring committee and a plan for reporting data monitoring committee findings to the IRB and the sponsor.

a. *Describe the plan to periodically evaluate the data collected regarding both harms and benefits to determine whether subjects remain safe.*

Subjects will be contacted the day after their pre- and post-test participation in the study to make sure that they did not experience unexpected or severe reactions to the vitamin supplement and optional lumbar puncture. A log will be kept to document the contact and relevant information from the subject. Subjects will also be given a 24-hour hotline to report any adverse event that they think is related to the study.

b. *Describe what data are reviewed, including safety data, untoward events, and efficacy data.*

Safety and untoward events related to the vitamin supplement and optional lumbar puncture will be reviewed.

c. *Describe how the safety information will be collected (e.g., with case report forms, at study visits, by telephone calls with participants).*

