Safety information will be collected by telephone calls or emails with the participants.

d. *Describe the frequency of data collection, including when safety data collection starts.*

Data will be collected by the researchers at baseline and the end of the study. Subjects will be instructed to contact the researchers as soon as possible if they experience any adverse events that they think is related to the study.

e. *Describe who will review the data.*

[name] will be the main person to review the data. He will consult with [name] or [name] if needed.

f. *Describe the frequency or periodicity of review of cumulative data.*

Cumulative data will be reviewed every month to ensure adherence to the approved protocol.

g. *Describe any conditions that trigger an immediate suspension of the research.*

If a subject reports an unexpected adverse event, the study will be suspended. The study will resume if it is determined that the event is unrelated to the study.

9. Withdrawal of Subjects

N/A

a. If applicable, describe anticipated circumstances under which subjects will be withdrawn from the research without their consent.
 
Click here to enter text.
	 N/A

b. If applicable, describe any procedures for orderly termination.
 
Click here to enter text.
	 N/A

c. If applicable, describe procedures that will be followed when subjects withdraw from the research, including partial withdrawal from procedures with continued data collection.
 
A subject who withdraws from the study on their own accord will be replaced by another. A subject who partially withdraws from procedures will remain in the study as long as they continue taking the supplement.
	 N/A

10. Risks to Subjects

a. List the reasonably foreseeable risks.

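### The only suspension rule (8g) has no severity criterion, so it can be read as not requiring a pause after a severe lumbar-puncture harm that 10a lists

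*Combined protocol and SAP*

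**What the plan says.** **Status of section 8.** It opens by declaring "This study involves no more than minimal risk study and this section is not required". Parts 8a to 8g are nevertheless filled in.

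**Detection and review.** Under 8a, subjects are contacted the day after each test visit to check for "unexpected or severe reactions to the vitamin supplement and optional lumbar puncture", and they have a round-the-clock hotline. Under 8b, "Safety and untoward events related to the vitamin supplement and optional lumbar puncture will be reviewed". Under 8d, subjects are told to "contact the researchers as soon as possible if they experience any adverse events that they think is related to the study". Under 8e, one investigator "will be the main person to review the data", with others to consult.

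**Suspension (8g).** The trigger is "If a subject reports an unexpected adverse event, the study will be suspended". The way back is "The study will resume if it is determined that the event is unrelated to the study".

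**Risks (10a).** The form's prompt is "List the reasonably foreseeable risks". The answer numbers seven possible side effects of the puncture, including spinal bleeding, infection, nerve damage and cerebral herniation. It also provides for caution in patients with possible raised intracranial pressure, a bleeding tendency or anticoagulation, or suspected epidural abscess, and for clinical judgment in deciding who has the puncture.

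**The concern.** A suspension rule matters most after the worst event the study can cause. Here that is a serious complication of a puncture done only for research (section 6a), which subjects may decline and for which they receive an extra $100 (section 11). The plan names those complications in advance. If naming them makes them expected, the one rule that compels a pause does not cover them.

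The people at stake are the subjects whose punctures come next. The precautions in 10a act before a puncture, one subject at a time. They do not say what happens to other subjects' punctures once a harm has occurred. Whether those are held would depend on discretion and on how the reviewer reads one undefined word.

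**Working it through.** No arithmetic applies beyond a count. The check sets the relevant sections side by side.

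**1. Is 8g the only rule?** Yes. The monthly review in 8f is aimed at protocol adherence and has no pause criterion. Items 9a (withdrawal without consent) and 9b (orderly termination) are marked not applicable. The mention of a monitoring committee in section 8 is form text, and no committee is set up.

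**2. What does the trigger contain?**

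| Element | 8g |
|---|---|
| Source of the report | The subject |
| Required property of the event | Unexpected (not defined) |
| Severity | Not mentioned |
| Relatedness | Not needed to suspend; used only for resuming |
| Consequence | The whole study is suspended |

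**3. Does the plan treat severity as separate?** In 8a it does. That wording joins the two properties with *or*, and the second adds something only if a reaction can be severe without being unexpected. The plan's own language thus admits a class of severe but not unexpected reactions. The follow-up call looks for that class; 8g does not act on it.

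**4. Do the puncture harms in 10a fall into that class?** It depends on the meaning of *unexpected*. Two readings are open:

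| Event | Reading A: listed in 10a means expected | Reading B: ordinary sense, in a study called minimal risk |
|---|---|---|
| Mild, unlisted reaction | Whole study suspended | Whole study may be suspended |
| Cerebral herniation or spinal bleeding after puncture | No pause required | Whole study suspended |
| Temporary headache after puncture | No pause required | Probably no pause |

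Reading A follows naturally from the foreseeable-risk prompt and from the contrast with 8a. Its result is inverted: a trivial unlisted event stops the study, while a herniation need not delay one further puncture. Reading B gives a sensible result. The protocol does not choose between them.

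**5. How many listed harms are affected?** Section 10a labels only some items as temporary, so the grading here is this review's own.

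- Serious by nature: spinal bleeding, cerebral herniation (2).
- Severe only in serious or persistent form: infection, nerve damage (2).
- Not grounds for a pause: procedural discomfort or pain, temporary headache, temporary back pain (3).

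Total: 2 + 2 + 3 = 7, which matches the list in 10a.

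**6. Who must report?** The staff contacts in 8a and 8c will usually elicit a report from the subject. A subject with a herniation or major bleed may be unable to give one, and the wording of 8g does not cover an event that staff learn of in another way.

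**The case against.** The strongest reply is that the gap rests on a definition the protocol does not give. The phrase about foreseeable risks is the form's prompt, not a statement by the investigators that listed events fall outside 8g. Their answer says only that side effects may include these harms, and they class the study as minimal risk. On an ordinary reading, a herniation in such a study is unexpected and 8g stops everything. The wording in 8a describes what a telephone call checks and does not define terms for 8g. This stands in part: Reading A is an inference, and the point cannot be put more strongly than that the rule *can be read* this way. But a safety rule whose answer depends on the reader is weakest at the moment it is needed.

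A second reply is that much is already in place: prompt contact, a hotline, review of puncture events, precautions before the puncture, and entry exclusions in section 3 for intracerebral hemorrhage, central nervous system malignancy and active central nervous system infection. This also stands, and it limits exposure and so the weight of the point. None of it supplies a rule for what follows a harm.

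A third reply concerns the remedy. As written, 8g is broad: it suspends the whole study for any unexpected event before relatedness is judged. A rewrite limited to events possibly related to the puncture or supplement, or one that stopped only the procedure concerned, would take protection away. That is correct, and the fix must add to 8g rather than replace it.

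**Conclusion.** The point holds as a minor-to-moderate safety matter. The trigger in 8g lacks the severity limb that 8a has, and with *unexpected* undefined it can be read as not requiring a pause after a severe puncture harm that 10a lists.

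A reader might infer more, and the documents do not support it:

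- *That the protocol lets punctures continue after a herniation.* It does not say so. A discretionary pause is not forbidden, and an investigator could treat the event as unexpected.
- *That severe harms would go unnoticed.* Sections 8a, 8b, 8d and 8e provide for detection and review.
- *That the risk to subjects is large.* No event rate or puncture uptake is given, so no frequency can be stated.

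The conclusion assumes that a listed harm may reasonably be taken as expected, and it uses this review's grading of the seven side effects. The primary endpoint, analysis and sample size are not affected.

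**What to change.** Keep the present rule, that any unexpected event suspends the whole study before relatedness is judged, and extend its trigger. For example:

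> The study is suspended after an unexpected or severe adverse event, reported by a subject or learned of by staff, whether or not it is listed in 10a. Spinal bleeding, cerebral herniation, persistent nerve damage and serious infection count as severe. Transient headache, transient back pain and procedural discomfort do not.

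This is an amendment to one paragraph and needs no extra staff or procedures. The downside is an occasional short pause after a severe but listed event. Under Reading A an unlisted event already triggers suspension, so the added pauses are confined to severe listed harms; under Reading B the worst of those harms are triggers already.

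One adjacent matter is left as it is: 8g states a route to resume only after an event found unrelated. The sponsor may wish to settle separately what happens after a related one, since a severe puncture harm would often be related.

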Subjects will be excluded if they had previous brain surgery or other severe neurological problems – intracerebral hemorrhage, traumatic brain injury, central nervous system malignancy, active CNS infection, significant stroke, Alzheimer disease or any type of implanted stimulator including but not limited to Deep Brain Stimulator (DBS) or pacemaker. All subjects must be without evidence of dementia, defined as a score > 24 the Mini-Mental State Examination and able to understand test instructions. Subjects must not have functional blindness (inability to participate in gait and visuomotor assessments) or lower limb amputation higher than the forefoot or any orthopedic problem that precludes performance of physical tests. Allergic to niacin. Significant cardiac, pulmonary, hepatic, gastrointestinal, or renal disease (e.g., New York Heart Association Class III or IV congestive heart failure; endocarditis; pulmonary insufficiency symptomatic at rest or with mild physical exertion; acute or chronic hepatitis; renal failure requiring dialysis; second and third degree AV block or sick sinus syndrome), or diabetes are also exclusionary factors.

4. Number of Subjects/Records/Samples Collected

Indicate the total number of subjects to be accrued/records reviewed/samples collected across all sites:

100

5. Recruitment Methods

Describe when, where, and how potential subjects will be recruited:

VA clinic (including medical records), word of mouth.

6. Procedures Involved

a. *Describe the procedures involved to include those procedures that are standard evaluation and/or care and those that are solely for research purposes:*

Standard procedures: basic physical examination for strength, speed, coordination, tremor, flexibility, rigidity and reaction time

Research procedures: questionnaire and tests to document health and cognitive status, blood, urine and spinal fluid samples, over-the-counter (non-prescription) vitamin B3 supplementation

b. Describe and explain the study design: Pre-post repeated measures placebo-controlled study

c. Describe the procedures performed to lessen the probability or magnitude of risks: Use of slow-release supplement to minimize potential skin itching

d. Describe the duration of an individual subject's participation in the study and the time involved: 6 months supplement study with a pre and post test, each lasting about 1 to 1.5 hr.

7. Data and Specimen Management

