
a. Describe the data analysis plan, including any statistical procedures: We will use the Unified Parkinson's Disease Rating Scale (UPDRS) III (Motor Section) as the primary pre- and post-treatment outcome assessment that is recommended for PD studies. Significant changes in outcome measures will be determined by performing a Mixed model analysis of variance, with Groups as the independent factor and Time as the repeated factor.
	 N/A												

b. When applicable, provide a power analysis: Based on the preliminary data using unpaired simple effects analyses, the minimum number of subjects needed per group to detect a statistical significance @ $p = .05$, 2-tailed and 80% power of detection are as follows:
 
  
 Outcome measures	Effect size (based on Cohen's d)	#	
   
 Subjects/group			
 
 UPDRS motor	1.46	14	
 
 Sleep efficiency (pilot data)	0.97	8	
  
 
The sample sizes are based on a large effect size, i.e., a grossly observable and clinically meaningful treatment effect. We have demonstrated that this is a reasonable expectation based on the actual effect sizes of the human preliminary data that we have shown. We used simple effects analyses as the basis for the sample size calculations because any sample size calculations based on the full design would require knowledge of the intra-class correlation across the treatments, as well as the carry-over, group, and period effects.
 
Correlation statistics. Based on the preliminary data's correlation coefficients (r) obtained via simple linear independent correlation tests comparing the variables versus disease severity (UPDRS motor section), the minimum number of subjects needed per group to detect a statistical significance @ $p = .05$, and 80% are as follows:
	Outcome measures	Effect size (based on Cohen's d)	#	Subjects/group			UPDRS motor	1.46	14	Sleep efficiency (pilot data)	0.97	8	 N/A
Outcome measures	Effect size (based on Cohen's d)	#											
Subjects/group													
UPDRS motor	1.46	14											
Sleep efficiency (pilot data)	0.97	8											

Outcome measures GPR109A levels Total Sleep Time Time to Fall Asleep Sleep Efficiency	r 0.59 -0.57 0.79 -0.73	# Subjects/group 20 18 8 10	

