Low-level temporary discomfort or pain during the blood and lumbar draw. Contraindications for the lumbar puncture: Although there are no absolute contraindications to performing the procedure, caution will be used in patients with the following conditions: 1) Possible raised intracranial pressure; 2) Thrombocytopenia or other bleeding diathesis (including ongoing anticoagulant therapy); 3) Suspected spinal epidural abscess. The side effects associated with lumbar puncture may include following: 1) Discomfort or pain during the procedure; 2) Bleeding into the spinal cord, particularly in people who take blood thinners or have a low platelet count (thrombocytopenia); 3) Temporary headache as a result of CSF leakage; 4) Infection; 5) Nerve damage; 6) Cerebral herniation; 7) Temporary back pain.

We will take a conservative approach in deciding which patient to include from the lumbar procedure. Overall, [name] will exercise his clinical judgment to exclude a subject from the procedure if, in his opinion, he feels that the subject presents with a set of conditions which renders them unsuitable for the procedure.

b. If applicable, describe any costs that subjects may be responsible for because of participation in the research.
 
Click here to enter text.
	 N/A

c. If applicable, describe risks to others who are not subjects.
 
Click here to enter text.
	 N/A

11. Potential Benefits to Subjects

Describe the potential benefits that individual subjects may experience from taking part in the research.

Niacin is an over-the-counter supplement. Our preliminary data indicates that PD patients will benefit from the supplementation. The dosage selected is 250 mg daily dose for 6 months. These dosages are low and do not produce any side effects. If at all, the PD patients will be benefitted by its actions. Subjects will be given a \$50 gift card for successfully completing the 6-month study. They will receive an additional \$100 if they participate in the spinal draw. At the end of the study, all subjects will receive the real niacin and be invited back for an optional follow-up assessment.

12. Confidentiality

Describe the procedures for maintenance of confidentiality.

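### Section 9c makes a partial withdrawer's place in the study depend on taking the supplement, which can lose 6-month UPDRS III outcomes selectively, and sections 6d, 7a, 8d and 9a do not settle the matter

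*Combined protocol and SAP*

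**What the plan says.** The prompt in section 9c asks what happens when subjects withdraw, "including partial withdrawal from procedures with continued data collection". The answer has two parts. First: "A subject who withdraws from the study on their own accord will be replaced by another". Second: "A subject who partially withdraws from procedures will remain in the study as long as they continue taking the supplement".

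Other sections bear on the same subjects:

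- **9a** asks: "If applicable, describe anticipated circumstances under which subjects will be withdrawn from the research without their consent". It is marked N/A.
- **6d** sets the schedule: "6 months supplement study with a pre and post test, each lasting about 1 to 1.5 hr". It attaches no adherence condition.
- **8d**, in the safety section, has the researchers gather data at the start and finish of the study, also without an adherence condition.
- **7a** makes UPDRS III the primary pre and post outcome, to be analysed by "performing a Mixed model analysis of variance, with Groups as the independent factor and Time as the repeated factor". It names no analysis set and no missing-data method.
- **7b** expects losses but gives no rate: "we propose to collect 30 PD subjects per group (total 60) to account for potential subject dropouts".
- **11** adds that, when the study ends, "all subjects will receive the real niacin and be invited back for an optional follow-up assessment".

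**The concern.** There is one post-treatment UPDRS III. A subject who leaves before it contributes no outcome to the placebo-controlled comparison. The optional assessment in section 11 cannot stand in for it, because by then everyone has been given niacin.

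If the subjects who go untested are those who stopped the supplement, the comparison drifts towards one of subjects who persisted. Replacing them restores the count but not the missing outcomes, and the plan does not say whether a replaced subject's data are used. A complete-case ANOVA drops such a subject from the Groups by Time test. A likelihood fit keeps the baseline value but relies on the outcome being missing at random. Section 7a does not say which is meant.

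Two things together produce bias: stopping must be related to UPDRS change, and either the stopping rates or the strength of that relation must differ between groups. Equal relations with unequal rates are enough. Section 6c chooses a slow-release product to limit itching, so more stopping on niacin is conceivable. Section 11 says that the dose has no side effects. The documents do not settle the direction.

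**Working it through.** **1. Who is covered**

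| Subject | 9c | 6d and 8d |
|---|---|---|
| Withdraws fully | Replaced; no post-test mentioned | Generic schedule |
| Drops some procedures, keeps supplement | Stays in | Post-test due |
| Drops some procedures, stops supplement | Out, as written | Post-test scheduled, no exception stated |
| Keeps all procedures, stops supplement | Not addressed | Post-test scheduled, no exception stated |

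The third row is a conflict and the fourth a gap. For the subjects that 9c covers, nothing in 6d or 8d overrides it.

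**2. The plan's own figure.** Section 7b gives 14 per group for d = 1.46 (two-sided .05, 80% power). A two-sample t-test gives 8.44, so 9; the 14 does not reproduce. That is a separate matter and nothing below uses it. The planned 30 per group is used.

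**3. Size of the bias.** From the plan: 30 per group, two-sided .05. Assumed, since the documents give nothing: stopping rate p of 20% niacin v 5% placebo, or 30% v 10%; correlation ρ = 0.3 or 0.5 between the tendency to stop and worsening; no true effect; a share f of stoppers has no post-test.

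With a normal latent tendency to stop, cut at z for rate p, the analysed subjects in a group look better than the whole group by f·ρ·φ(z)/(1 − f·p) SD of change. The bias is the difference between groups.

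Example, f = 1, 20% v 5%: φ(z)/(1 − p) is 0.350 for niacin and 0.1086 for placebo. The difference is 0.2414; times 0.3 gives 0.072 and times 0.5 gives 0.121.

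| Share lost, f | 20% v 5% (ρ = 0.3 / 0.5) | 30% v 10% (ρ = 0.3 / 0.5) | Type I error, complete case |
|---|---|---|---|
| 1 | 0.072 / 0.121 | 0.091 / 0.151 | 5.7% to 8.2% |
| 0.5 | 0.031 / 0.051 | 0.034 / 0.056 | 5.1% to 5.7% |
| 0.25 | 0.014 / 0.024 | 0.015 / 0.025 | 4.7% to 5.2% |

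The bias is in SD of change and favours niacin. Type I error is simulated (20,000 trials per setting, pooled t-test on change). The rows f = 0.5 and 0.25 represent the literal reading of 9c, in which only some stoppers are also partial withdrawers.

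**4. Variations**

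- All stoppers untested and replaced up to 30 persisters per group: type I error 5.9% to 9.3%.
- All stoppers untested, likelihood fit, assumed pre-post correlation 0.5 to 0.8: bias about 0.05 to 0.14 SD, type I error 5.3% to 7.3%.
- Stopping related to baseline only: likelihood bias zero to two decimals; complete-case bias 0.02 to 0.08 SD, against niacin.
- Excess stopping unrelated to outcome: bias zero, type I error about 5%.
- More stopping on placebo: the sign reverses.

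**5. Power if stoppers are kept.** Assume that 30% of the niacin group stop and lose all benefit, so the mean effect is 0.7d.

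- d = 1.46: 0.7 × 1.46 = 1.02. Power at 30 per group is 97% by t-test at that shift, and 94% when the added variance of a 70/30 mixture is simulated.
- Section 7b does not say which SD its d uses. If it is the raw-score SD, d for change is 1.46/√(2(1 − r)), which is 1.23, 1.46 or 2.31 for pre-post correlation r = 0.3, 0.5 or 0.8. Power at 0.7d is 91%, 97% or over 99%. At r = 0.3 the mixture raises the niacin variance to 1 + 0.3 × 0.7 × 1.23² = 1.32, and simulated power is about 86%.
- d = 0.74, which has 80% power at 30 per group with no stopping: 48% to 51%.

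**The case against.** The strongest reply is that 9c is a retention clause. It concerns subjects who decline some procedures, the lumbar puncture is optional, and the evident purpose may be to keep such subjects in. Sections 6d and 8d schedule the final assessment for everyone, and 9a marked N/A suggests that nobody is to be removed against their will. On that view the default is that stoppers are tested, and only an explicit sentence is missing.

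Much of this stands. A reader might infer that 9c puts every subject who stops the supplement out of the study, or that nothing in the plan schedules a 6-month UPDRS III for them. The documents support neither: 9c is confined to partial withdrawers, and the schedule has no adherence condition. Under the literal reading the assumed effect is small. The missing analysis set in 7a would also be a weakness whatever 9c said.

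What does not stand is that 6d and 8d cure the problem. The prompt in 9c raises continued data collection, and the answer makes continued participation conditional on the supplement. For a partial withdrawer who stops, a specific rule ends participation, while 6d is generic and 8d is generic and concerned with safety. Site staff following 9c would have no reason to call that subject back.

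**Conclusion.** The concern holds in a limited form. Section 9c, followed as written, loses the primary outcome for partial withdrawers who stop the supplement, and it leaves other stoppers undecided. The four sections do not agree on what happens, and 7a does not define whom the analysis includes.

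The likely size is modest: about 0.01 to 0.06 SD of change, with type I error near nominal, if a quarter to a half of stoppers are lost. The larger range of 0.07 to 0.15 SD needs every stopper to go untested, which 9c does not say. All of these figures rest on assumed stopping rates and correlations. The true size and direction cannot be found from the documents, and the bias is zero if stopping is unrelated to outcome. It should still be corrected, because a 6-month outcome not collected at the time cannot be recovered and the correction is cheap.

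**What to change.** 1. Reword 9c, and bring 9a, 6d and 8d into line with it, so that stopping the supplement does not count as withdrawal from the study. Every PD subject assigned to a group who has not withdrawn consent is asked to attend the 6-month UPDRS III that 6d already schedules. A replacement is an addition, and the data of the subject replaced are kept.
2. State in 7a that the primary analysis includes all PD subjects in their assigned group, with an analysis of subjects who continued the supplement as a sensitivity analysis.

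This concerns outcome assessment only and sets no rule on when a subject should stop.

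**Gain.** Subjects who withdraw consent stay missing, so the bias is reduced rather than removed. From the case in which all stoppers are untested, it falls to 0.03 to 0.06 SD if half attend and to zero if all do.

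**Cost.** Two wording changes, and at most about 8 to 12 post-tests among subjects who stopped (30 × 0.20 + 30 × 0.05 = 7.5; 30 × 0.30 + 30 × 0.10 = 12). These visits are already in the schedule. The real price is dilution by non-adherence: affordable at the protocol's d = 1.46, but with 30% stopping and no retained benefit, power is about half if the true d is 0.74.

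### Section 10a allows an optional, research-only lumbar puncture in subjects with three named risk conditions, subject only to caution and one clinician's opinion

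*Combined protocol and SAP*

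**What the plan says.** - **Status of the puncture.** Section 6a separates standard from research procedures and puts spinal fluid on the research side: "Research procedures: questionnaire and tests to document health and cognitive status, blood, urine and spinal fluid samples". Section 8a provides for contact with subjects the day after testing, to ask about "unexpected or severe reactions to the vitamin supplement and optional lumbar puncture".
- **Rule on risk conditions.** Under a label announcing contraindications, Section 10a says: "Although there are no absolute contraindications to performing the procedure, caution will be used in patients with the following conditions". The three conditions are possible raised intracranial pressure; thrombocytopenia or another bleeding tendency, with current anticoagulant treatment included; and suspected spinal epidural abscess.
- **Selection for the puncture.** Section 10a continues: "We will take a conservative approach in deciding which patient to include from the lumbar procedure". One clinician is to "exercise his clinical judgment to exclude a subject from the procedure if, in his opinion", the subject's conditions make the procedure unsuitable.
- **Stated harms.** Section 10a lists seven side effects. One is "Bleeding into the spinal cord, particularly in people who take blood thinners or have a low platelet count". Nerve damage and cerebral herniation are also listed.
- **General eligibility.** Section 3 excludes, among others, people with "intracerebral hemorrhage, traumatic brain injury, central nervous system malignancy, active CNS infection, significant stroke". It also excludes significant cardiac, pulmonary, hepatic, gastrointestinal or renal disease, and diabetes.
- **Benefit and payment.** Section 11 expects benefit from niacin. For the spinal draw it offers $100, on top of a $50 gift card for completing the study.

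**The concern.** A clinician may reasonably accept a relative contraindication when the puncture result will guide that patient's care. Nothing in these documents says that this puncture does so. Its stated purpose is to look for evidence of inflammation, and Section 11 claims no personal medical benefit from it. The case for proceeding in a subject with a recognised risk condition is therefore weak, while the harms listed in Section 10a include serious ones.

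The protocol identifies who is at higher risk of spinal bleeding and then does not keep those people out. Two clinicians following the text faithfully could reach opposite decisions about the same anticoagulated subject. The safeguards elsewhere come too late to help: the next-day contact and the 24-hour hotline in Section 8a detect harm after the needle has gone in.

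**Working it through.** No figure in the plan bears on this point, so the check compares Section 10a with the places where a mandatory rule could stand.

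**Step 1. Does any safeguard in Section 10a set a criterion?** It states three: caution, a conservative approach, and the clinician's opinion. None gives a condition, test result or medication that decides the matter. Safeguards with a criterion: 0 of 3.

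**Step 2. Is any named condition a mandatory bar, in Section 10a or through Section 3?**

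| Condition in 10a | Response in 10a | Nearest cover in Section 3 | Mandatory puncture exclusion in 10a? |
|---|---|---|---|
| Possible raised intracranial pressure | Caution | Partial: hemorrhage, malignancy, brain injury, CNS infection and significant stroke may remove some causes | No |
| Low platelets, other bleeding tendency, anticoagulants | Caution | Incidental: hepatic or cardiac exclusions may remove some people; none of the three elements is named | No |
| Suspected spinal epidural abscess | Caution | Partial: active CNS infection may be read to cover some cases | No |

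Mandatory exclusions in Section 10a: 0 of 3. Conditions named in Section 3: 0 of 3. Elements of the second condition named in Section 3: 0 of 3.

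The partial cover is less certain for controls. The inclusion text of Section 3 plans to recruit controls with traumatic brain injury or stroke, while its exclusion text rules out traumatic brain injury and significant stroke. How fully those exclusions apply to controls is unclear.

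**Step 3. Does the protocol itself link a condition to a harm?** Of the seven side effects in Section 10a, it ties one, spinal bleeding, to a condition it names. It lists herniation but does not connect it to raised pressure. The link that can be shown from the documents alone therefore concerns the second condition, which is also the one with no named cover in Section 3.

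**Step 4. Does a later safeguard prevent the harm?** The contact and hotline in Section 8a follow the puncture. Section 8g suspends the study after an unexpected adverse event, which is also after the fact. A side effect already listed in Section 10a might not count as unexpected.

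**Step 5. What follows for a subject on an anticoagulant?** Section 3 does not exclude this person for that reason. Section 10a calls for caution and leans towards leaving the person out, but does not require it. As written, the puncture may go ahead.

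**The case against.** The strongest reply is that the discretion already points one way. Section 10a answers a prompt about foreseeable risks and is not an eligibility section. Even so, it names the conditions, promises conservatism and gives the clinician power to exclude. The protocol never says that an anticoagulated subject will be punctured, and no expected exposure can be shown. This is fair as far as it goes: the text leans towards exclusion, and nothing here suggests that the clinician would act carelessly. But Section 10a is the only place in the supplied documents that governs selection for the puncture. If exclusion is the intent, it is easy to write down.

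A second reply is that the three conditions do not carry equal weight. Possible raised pressure and suspected abscess are matters of judgement by their own wording, and Section 3 removes some such people. This stands: the case is strongest for bleeding tendency and anticoagulants. Barring the puncture when the clinician does suspect one of the other two conditions is still sound.

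A third is that the remedy sets no platelet threshold, no age limit for a result on record and no rule for recently stopped anticoagulants. This also stands as a limit. The remedy fixes what follows from a known condition and does not detect unknown ones.

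Finally, the puncture is optional, and Section 13 says that consent covers risks and the right to stop. The consent pages are not in the supplied text, so any screening wording there cannot be checked. Consent does not replace a rule for the person doing the puncture.

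**Conclusion.** The concern holds. Section 10a names three risk conditions and makes none of them a mandatory exclusion from an optional research puncture, and Section 3 does not close the gap. It is widest for low platelets, bleeding tendency and anticoagulant treatment, where the protocol states the added risk itself and Section 3 names no criterion.

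The size can be given only as these counts. Puncture uptake, the number of punctures per subject and the frequency of anticoagulant use are not in the documents, and none is assumed. The conclusion rests on Sections 3, 6a, 8, 10a and 11 as supplied, and on there being no overriding rule in the removed consent pages. The point concerns subject safety and does not touch the validity of the UPDRS III analysis. The change should be made because the protection is real and the cost is small. Confidence is medium.

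**What to change.** In Section 10a, replace the sentence that says no contraindication is absolute with a statement that the research lumbar puncture will not be done in any subject with one of the three conditions, and keep the list as it is. After the list, add:

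- Before any puncture, the clinician records yes or no for each condition, using history, current medication and any platelet or coagulation result on record.
- Any yes means no puncture.
- Subjects excluded from the puncture continue with the other procedures only if they still meet the Section 3 criteria.

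Keep the sentences on conservatism and clinical judgement, so that they govern any further exclusions beyond the list.

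The cost is a wording change and a three-item check, with no new test. Some spinal fluid samples will be lost to the inflammation aims, the spinal fluid results will describe lower-risk subjects, and those excluded will not receive the $100. No one leaves the UPDRS III analysis unless Section 3 already makes them ineligible. Two limits remain: possible raised pressure and suspected abscess are still clinical judgements, and low platelets that appear in no record would still be missed.
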